6.3.1 Primary Efficacy Endpoint

Subjects are instructed to report headache occurrence, headache pain features and associated symptoms, aura occurrence, and medication used to treat headache or aura in the eDiary headache report every day in the OP and DBT Phase.

Migraine days per month are assessed as "migraine days per 4 weeks" to correspond with the 4-week visit schedule. Migraine days per month are based on 4-week intervals, and are prorated to account for missing migraine reports.

See Section 9.2.2 for the definition of eDiary efficacy data days, and Section 9.2.5 for the definition of migraine days.

The number of migraine days per month in the DBT Phase is examined relative to the number of migraine days per month in the OP for the migraine analysis set, i.e., subjects with ≥ 14 days of eDiary efficacy data in both the OP analysis period and ≥ 1 month (i.e., 4-week interval) in the on-DBT efficacy analysis period.

Months in the DBT Phase are defined as follows:

- Month 1: \leq 4 weeks; study days 1 to 28
- Month 2: > 4 to ≤ 8 weeks; study days 29 to 56
- Month 3: > 8 to ≤ 12 weeks; study days 57 to 84.

Analyses are based on eDiary efficacy dates in the OP and on-DBT efficacy analysis periods.

The number of migraine days per month is prorated to 28 days and derived as follows:

- OP: 28 × (total number of migraine days in the OP analysis period)/(total number of eDiary efficacy data days in the OP analysis period). Subjects must have ≥ 14 days of eDiary efficacy data (not necessarily consecutive) in the OP to be evaluable.
- Month (i.e., 4-week interval) in the on-DBT efficacy analysis period: 28 × (total number of migraine days in the month)/(total number of eDiary efficacy data days in the month).
 Subjects must have ≥ 14 days of eDiary efficacy data (not necessarily consecutive) in the specified month to be evaluable.
- Overall DBT: 28 × (total number of migraine days through Month 3 in the on-DBT efficacy analysis period)/(total number of eDiary efficacy data days through Month 3 in the on-DBT efficacy analysis period).

6.3.1.1 Missing Efficacy Data

The frequency table of missing efficacy data in the OP and DBT Phase is provided for the DBT efficacy analysis set, and displays the following categories:

- Included in the migraine analysis set: ≥ 14 days of eDiary efficacy data in both the OP and ≥ 1 month (i.e., 4-week interval) of the DBT Phase
 - Month 1: \leq 4 weeks *
 - Month 2: > 4 to ≤ 8 weeks *
 - Month 3: > 8 to ≤ 12 weeks *
- Excluded from the migraine analysis set
 - < 14 days of eDiary efficacy data in the OP

 - < 14 days of eDiary efficacy data in all 3 months of the DBT Phase.

In the categories marked with "*", subjects must have ≥ 14 days of efficacy data (not necessarily consecutive) in the specified month to be evaluable.

6.3.1.2 Migraine Days per Month Changes From OP Over Time on DBT: Descriptive Analyses

The table of values and changes (both absolute and percent) from the OP in the number of migraine days per month in the DBT Phase is provided for the migraine analysis set, and summarizes parameters descriptively as continuous variables (including 2-sided normal 97.5% CIs for mean change) by treatment group and by pain intensity in each month of the DBT Phase and overall DBT. Pain intensity categories are (1) total (mild, moderate, severe, or not reported) and (2) moderate or severe. The table also displays results by subgroup level for all efficacy subgroups of interest described in Section 4.3.

In the percent change analyses, subjects must also have ≥ 1 migraine day (i.e., absolute not prorated) of appropriate pain intensity in the OP analysis period to be included.

6.3.1.3 Migraine Days per Month Changes From OP Over Time on DBT: Treatment Group Comparisons

Analyses are based on the migraine analysis set and total pain intensity, unless otherwise specified.

Main Analysis: Migraine Analysis Set

The main analysis of the primary endpoint uses a linear mixed effects model with repeated measures and the following attributes:

- Variables: change from the OP in number of total migraine days per month as the dependent variable; number of total migraine days per month in the OP as a covariate; treatment group, randomization stratum, categorical month (i.e., Months 1 to 3 of the DBT Phase), and the month-by-treatment group interaction as fixed effects.
- Covariance structure for repeated measures accounting for within-subject correlated errors:
 assumed to be homogeneous across treatment groups, and initially specified as unstructured.
 If the model fails to converge or cannot be fit with an unstructured covariance structure, then
 other covariance structures are specified in the following hierarchical order: Toeplitz (which
 has heterogeneous variances and heterogeneous correlations between elements); first-order
 autoregressive with heterogeneous variances; and first-order autoregressive with
 homogeneous variances.
- SE estimation method: Huber-White "sandwich" (refer to the Core SAP).

The table displays the following model estimates:

- Least-squares mean (LSM) change from OP, SE, and 97.5% CI by month and overall DBT for each treatment group
- Difference in LSM changes from OP between each rimegepant treatment group and placebo (rimegepant_i placebo; i = 1 and 2), SE, 97.5% CI, and p-value at each month and overall DBT. Results in the overall DBT support the primary objective, results in the last month

support secondary objective #2, results in the first month support secondary objective #3, and results in the second month support exploratory objective #1.

See Section 9.3.1 for example SAS code. Model estimates by randomization stratum (yes, no) are presented in the same table, using additional models that exclude randomization stratum as a fixed effect.

These main analyses are repeated for moderate or severe pain intensity to support exploratory objective #1. All variables in the model are the same, except (1) change from the OP in number of moderate or severe migraine days per month is the dependent variable, and (2) number of moderate or severe migraine days per month in the OP is the covariate. The corresponding table has the same format.

A line plot with error bars displays the LSM change from OP in the number of total migraine days per month on the y-axis versus month of the DBT Phase on the x-axis by rimegepant treatment group. Error bars denote 97.5% CIs for LSM changes.

J2R Imputation Sensitivity Analysis: DBT Efficacy Analysis Set

A sensitivity analysis of the primary endpoint uses the same model as the main analysis, but with jump to reference (J2R) to impute missing data (i.e., change from OP in the number of total migraine days per month) in Months 1 to 3 for the DBT efficacy analysis set. Placebo is considered the "reference".

The analysis is performed using the following steps:

- 1) Data are imputed under J2R using specific multiple imputation SAS macros for n = 30 data sets.^{1,2}
 - a) Subjects with < 14 days of eDiary efficacy data in a specified month in the on-DBT efficacy analysis period have missing data imputed in that month.
 - b) Data imputation is applied to each treatment group.
 - c) The imputation model uses the following variables: number of total migraine days per month in the OP, age, sex, race, randomization stratum, and treatment group. Race may be reduced to fewer levels (e.g., white versus non-white) based on the availability of data.
 - d) The macros are run in the following order: %part1A; %part1B using n = 200 data sets (Ndraws parameter) and n = 10 as the length of the Markov chain Monte Carlo (MCMC) chain thinning (thin parameter); %part2A; and %part2B. Note that the Ndraws and thin parameters may be modified as needed (e.g., to decrease Monte Carlo error and autocorrelation).
- 2) Each imputed data set in step 1 is analyzed using the same model from the main analysis (see Section 9.3.1).
- 3) Results from each model analysis in step 2 are combined to produce a pooled difference in LSM change, SE, 97.5% CI, and p-value using SAS proc mianalyze.

The corresponding table has the same format as the one for the main analysis.

Tipping Point Sensitivity Analysis: DBT Efficacy Analysis Set

A tipping point sensitivity analysis is performed for each rimegepant treatment group separately for the DBT efficacy analysis set, and only if the p-value ≤ 0.025 for that rimegepant treatment group comparison to placebo for the main analysis of the overall DBT.

The analysis is performed for a rimegepant_i treatment group (i = 1 or 2) using the following steps:

- 1) A shift parameter of $\delta = 0$ is selected.
 - a) Data are imputed under the missing not at random (MNAR) assumption for the rimegepant_i treatment group with a shift adjustment and the missing at random (MAR) assumption for all other treatment groups using SAS proc mi for n = 30 data sets.^{1,2}
 - i) Subjects with < 14 days of eDiary efficacy data in a specified month in the on-DBT efficacy analysis period have missing data imputed in that month.
 - ii) Data imputation is applied to each treatment group.
 - iii) The fully conditional specification (FCS) method is used with regression to impute data at Months 1 to 3.
 - iv) The imputation model specifies variables in the following order: changes from OP in the number of total migraine days per month at Months 1 to 3, number of total migraine days per month in the OP, age, sex, race, randomization stratum, and treatment group. Race may be reduced to fewer levels (e.g., white versus non-white) based on the availability of data.
 - v) A shift of δ is applied to imputed data only for subjects in the rimegepant_i treatment group.
 - b) Each imputed data set in step 1a is analyzed using the same model from the main analysis (see Section 9.3.1).
 - c) Results from each model analysis in step 1b are combined to produce a pooled difference in LSM change, SE, 97.5% CI, and p-value using SAS proc mianalyze.
- 2) The p-value for the rimegepant_i treatment group comparison to placebo of the overall DBT is compared to 0.025.
 - a) If p-value ≤ 0.025 , then δ is incremented by 0.1, and step 1 is repeated.
 - b) If p-value > 0.025, then the iterative process stops, and the last δ used becomes the tipping point.

For each shift parameter, the same statistics are provided as those in the main analysis, but only for the overall DBT and not by randomization strata. Results across all shift parameters are displayed together in the same table.

6.3.2 Secondary Efficacy Endpoints

6.3.2.1 Percentages of Subjects With Reduction From OP in Number of Migraine Days per Month Over Time on DBT

Analyses are based on the migraine analysis set with eDiary efficacy data dates in the OP and on-DBT efficacy analysis periods (see Section 7.2).

In analyses by months, subjects must (1) achieve the reduction criterion from OP in the number of migraine days per month in the specified month, (2) have \geq 14 days of eDiary efficacy data (not necessarily consecutive) in the specified month, and (3) have \geq 1 migraine day (absolute not prorated) of appropriate pain intensity in the OP analysis period to be classified as responders in the specified month. Otherwise, subjects are classified as failures in the specified month.

In analyses of the overall DBT, subjects must (1) achieve the reduction criterion from OP in the number of migraine days in the overall DBT, and (2) have ≥ 1 migraine day (absolute not prorated) of appropriate pain intensity in the OP analysis period to be classified as responders. Otherwise, subjects are classified as failures.

Treatment Group Comparisons

For each pain intensity (total; moderate or severe) and select percentage reduction ($\geq 50\%$, \geq 75%, and 100%), the percentages of subjects with reductions in the number of migraine days per month are compared between each rimegepant treatment group and placebo using Mantel-Haenszel risk estimation with stratification by randomization stratum (yes, no). Percentages are calculated against the number of subjects in the migraine analysis set.

The table displays the following statistics at each month of the DBT Phase and overall DBT by pain intensity:

- Response rate (i.e., "n/N" and percentage), ASE, and 97.5% CI for each treatment group
- Stratified percentage difference between each rimegepant treatment group and placebo (rimegepant_i placebo; i = 1 and 2), ASE, 97.5% CI, and p-value
- Response rate (i.e., "n/N" and percentage), ASE, and 97.5% CI by randomization stratum for each treatment group
- Percentage difference between each rimegepant treatment group and placebo (rimegepant_i placebo; i = 1 and 2), ASE, 97.5% CI, and p-value by randomization stratum.

Results for the endpoint of \geq 50% reduction of moderate or severe pain intensity in the overall DBT support secondary objective #1. Results for all other endpoints support exploratory objective #2.

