3.2 Estimands

An estimand is the target of estimation to address the scientific question of interest posed by a study objective. The 4 attributes of an estimand include the population of interest, endpoint of interest, summary of the endpoint, and specification of how intercurrent events are reflected in the scientific question of interest.

For all objectives, the population of interest is defined through appropriate inclusion/exclusion criteria to reflect the targeted patient population for approval. Refer to the protocol for inclusion/exclusion criteria.

Intercurrent Events

Intercurrent events are those that occur after treatment initiation and either preclude observation of the endpoint or affect its interpretation.

Study drug discontinuation before the time point of interest defining the endpoint is considered an intercurrent event.

- For efficacy objectives assessed with a continuous endpoint during the DBT Phase, study drug discontinuation is handled with a "hypothetical strategy," i.e., the hypothetical scenario is that had subjects not discontinued DB study drug, their efficacy would have been similar to the efficacy of subjects from the same treatment group and randomization stratum who did not discontinue DB study drug. All observed values of the endpoint of interest are excluded after DB study drug discontinuation (see Section 7.2), and statistical methods are used to estimate the treatment effect that would have been seen had the intercurrent event not occurred.
- For efficacy objectives assessed with a binary endpoint during the DBT Phase, DB study drug discontinuation is handled with a "composite strategy," i.e., the occurrence of the intercurrent event is integrated as a component of the endpoint. All observed values of the endpoint of interest are excluded after DB study drug discontinuation (see Section 7.2), and subjects with missing data are considered failures.
- For safety objectives, study drug discontinuation is handled with a "while-on-treatment strategy," i.e., response to treatment prior to the occurrence of the intercurrent event of

interest, such that all observed values of the endpoint of interest are used prior to study drug discontinuation plus 7 days (see Section 7.2 and the Core SAP).

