3.2.2 Secondary Objective Estimands

The estimands corresponding to the secondary objectives are shown in Table 2.

Table 2 Secondary Objective Estimands

| Objective 1 | Proportion of subjects with $\geq 50\%$ reduction from the OP in the number of moderate or severe migraine days per month over the entire DBT Phase | |
|---------------------|---|--|
| Efficacy Endpoint | Proportion of subjects with $\geq 50\%$ reduction from the OP in number of moderate or severe migraine days per month over the entire DBT Phase (Weeks 1 to 12) | |
| Summary | Percentage by treatment group and difference in percentages between treatment groups using Mantel-Haenszel risk estimation for the migraine analysis set | |
| Intercurrent Events | Study drug discontinuation: composite strategy | |
| | Nonstudy prophylactic migraine medication use: treatment policy strategy | |
| | Nonstudy acute migraine-specific medication use: composite strategy | |
| | Use of nonstudy other medication to treat headache (migraine or nonmigraine) or aura: treatment policy strategy | |
| Objective 2 | Mean reduction from the OP in the number of migraine days per month in the last 4 weeks of the DBT Phase | |

| Efficacy Endpoint | Mean change from the OP in the number of migraine days per month in the last 4 weeks (Weeks 9 to 12) of the DBT Phase | |
|----------------------------|---|--|
| Summary | Mean change from the OP by treatment group using descriptive statistics and linear mixed effects model with repeated measures, and difference between treatment groups from model for the migraine analysis set | |
| Intercurrent Events | Study drug discontinuation: hypothetical strategy | |
| | Nonstudy prophylactic migraine medication use: treatment policy strategy | |
| | Nonstudy acute migraine-specific medication use: composite strategy | |
| | Use of nonstudy other medication to treat headache (migraine or nonmigraine) or aura: treatment policy strategy | |
| Objective 3 | Mean reduction from the OP in the number of migraine days per month in the first 4 weeks of the DBT Phase | |
| Efficacy Endpoint | Mean change from the OP in the number of migraine days per month in the first 4 weeks (Weeks 1 to 4) of the DBT Phase | |
| Summary | Mean change from the OP by treatment group using descriptive statistics and linear mixed effects model with repeated measures, and difference between treatment groups from model for the migraine analysis set | |

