7.2 Analysis Periods

Measurements are slotted into analysis periods based on comparing measurement dates to analysis period reference dates (time is not applicable).

Analysis periods are defined according to endpoints as follows:

• eDiary efficacy endpoints (migraine days, acute migraine-specific medication days, acute migraine medication days, headache days)

- OP: eDiary efficacy data date on or after the OP start date through the OP end date. Note that this is a subset of the pretreatment analysis period.
- 28-day OP: eDiary efficacy data date on or after the OP start date through the earlier of {OP start date + 27 days; OP end date}. Note that this is a subset of the OP analysis period, and is used only to assess efficacy data issues during the OP as relevant protocol deviations.
- o On-DBT efficacy:
 - If the DB study drug last date or OL rimegepant start date is not missing: eDiary efficacy date on or after the DB study drug start date through the earlier of {DB study drug last date; OL rimegepant start date 1 day}
 - If the DB study drug last date and OL rimegepant start date are both missing: eDiary efficacy data date on or after the DB study drug start date

This period is used to assess efficacy during the DBT Phase.

- Pretreatment characteristics and safety endpoints *
 - Pretreatment: This period is used to derive baseline values
 - On-DBT safety: This period is used to assess safety endpoints on DBT for the DBT safety analysis set.
 - Post-DBT pre-OL rimegepant safety: This period is used to assess safety endpoints during the interim period (i.e., post-DBT pre-OL rimegepant) for the interim safety analysis set.
 - On-OL rimegepant safety: This period is used to assess safety endpoints on OL rimegepant for the OL rimegepant safety analysis set.
 - On-DB or OL rimegepant safety: This period is used to assess safety endpoints on DB or OL rimegepant for the DB or OL rimegepant safety analysis set.
 - On-treatment safety: This period is used to derive analysis visit windows for slotting
 measurements and may also be used to assess blinded safety endpoints on treatment in an
 integrated safety report, as needed.
 - Follow-up safety: This period is used to assess safety endpoints during follow-up for the follow-up safety analysis set.
- Outcomes research endpoints (MSQoL, SM, CGI-c) *
 - DBT outcomes research: This period is used to assess outcomes research endpoints during the DBT Phase for the DBT efficacy analysis set.

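### First gated secondary endpoint (≥50% responder, Weeks 1 to 12): the SAP declares a composite strategy for study drug discontinuation, but its overall-DBT responder rule does not implement it

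*SAP*

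**What the plan says.** **Declared strategy.** For secondary objective 1, SAP Table 2 lists "Study drug discontinuation: composite strategy". SAP 3.2 explains that for binary efficacy endpoints this means "the occurrence of the intercurrent event is integrated as a component of the endpoint". It adds that values after discontinuation are excluded "and subjects with missing data are considered failures". Protocol 9.3.1.2 likewise imputes missing data for this endpoint as non-response.

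**Operational rule.** SAP 6.3.2.1 gives two responder rules.
- By month: the subject must meet the reduction criterion, have at least 14 diary days in that month, and have at least one qualifying migraine day in the Observation Phase. Anyone else is a failure for that month.
- Overall: "In analyses of the overall DBT, subjects must (1) achieve the reduction criterion from OP in the number of migraine days" over the whole phase, and must have at least one qualifying migraine day in the Observation Phase. There is no third condition.

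**Data window.** SAP 7.2 defines the on-DBT efficacy period as "eDiary efficacy date on or after the DB study drug start date through the earlier of" the last double-blind dose and the day before open-label start. SAP 6.3.1 computes the overall value as 28 × ("total number of migraine days through Month 3 in the on-DBT efficacy analysis period") divided by the diary days in the same period. Month 3 is "study days 57 to 84".

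**The concern.** A composite strategy requires that stopping study drug in itself determines the outcome. The overall rule never asks whether the subject stopped. It looks only at the days before stopping and scales them to 28. SAP 3.2 has a name for this in its safety paragraph, the while-on-treatment strategy: "response to treatment prior to the occurrence of the intercurrent event of" interest. The declared estimand and the programmed one therefore differ.

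This is the first test after the primary in each regimen's hierarchy (Protocol 9.3.1.3, SAP 5). If the primary is significant and this result lies near the threshold, the choice of rule could decide whether the four later efficacy and outcomes endpoints can be tested. The jump-to-reference and tipping-point analyses in SAP 6.3.1.3 cover only the primary endpoint, so no planned sensitivity analysis addresses this one.

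**Working it through.** **Step 1. Can an early stopper have a missing overall value?** The migraine analysis set (SAP 4.1, with SAP 6.3.1) requires at least 14 diary days in the Observation Phase and in at least one 4-week interval of the on-DBT efficacy period. The denominator of the overall value is therefore at least 14 for every subject analysed. The value always exists, so missing-equals-failure has nothing to act on.

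**Step 2. Worked case (invented subject).** The Observation Phase has 8 moderate or severe migraine days per 28. The subject stops after study day 14 with 14 diary days, 2 of them moderate or severe migraine days.
- Overall value = 28 × 2/14 = 4.0. Reduction = 1 − 4.0/8 = 50%. The subject is a Weeks 1 to 12 responder.
- By-month rule: failure in Months 2 and 3 (0 diary days, fewer than 14).
- Declared composite: failure overall.

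**Step 3. Effect on rates.** The plan gives no power, response rate or discontinuation rate for this endpoint. Its one power figure concerns the primary and reproduces: 1.1/(3.5 × √(2/200)) = 3.143; 3.143 − 2.241 = 0.901; Φ(0.901) = 0.816, against the stated roughly 80%. The drop from 220 randomized to roughly 200 in the migraine set counts subjects outside the set, not stoppers within it.

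Let c be the completer response rate, d the share of the migraine set stopping early, and r the share of stoppers meeting the criterion on partial data.
- Rule as written: arm rate = c(1 − d) + r×d
- Composite: arm rate = c(1 − d)
- Rise in each arm: r×d
- Shift in the difference: rR×dR − rP×dP (R = rimegepant, P = placebo)

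Illustration, all rates assumed: c = 50% rimegepant and 40% placebo, 200 per arm, 2-sided alpha 0.025 (z = 2.2414), normal approximation with unpooled SE.

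| d (R/P) | r (R/P) | Difference, as written | Difference, composite | Shift | Power, as written / composite |
|---|---|---|---|---|---|
| 10%/10% | 20%/20% | 47.0 − 38.0 = 9.0 | 45.0 − 36.0 = 9.0 | 0 | 0.34 / 0.34 |
| 15%/10% | 20%/30% | 45.5 − 39.0 = 6.5 | 42.5 − 36.0 = 6.5 | 0 | 0.18 / 0.18 |
| 15%/10% | 20%/20% | 45.5 − 38.0 = 7.5 | 42.5 − 36.0 = 6.5 | +1.0 | 0.24 / 0.18 |
| 10%/15% | 20%/20% | 47.0 − 37.0 = 10.0 | 45.0 − 34.0 = 11.0 | −1.0 | 0.42 / 0.51 |
| 10%/10% | 40%/20% | 49.0 − 38.0 = 11.0 | 45.0 − 36.0 = 9.0 | +2.0 | 0.50 / 0.34 |
| 10%/10% | 20%/40% | 47.0 − 40.0 = 7.0 | 45.0 − 36.0 = 9.0 | −2.0 | 0.20 / 0.34 |

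Differences and shifts are in percentage points. The shift can take either sign. In the second row both d and r differ between arms, yet the shift is zero.

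**The case against.** **The general missing-data rule already covers it.** SAP 3.2 and Protocol 9.3.1.2 count missing data as failure, and SAP 6.3 says binary results incorporate missing-data imputation. A stopper has no Month 2 or Month 3 data, so a programmer could fail that subject on this ground. This shows the intention may have been composite. It does not settle the matter: SAP 6.3.2.1 states the overall rule in full, omits the 14-day condition that it has just set by month, and rests on a value that is never missing. At the least, the sections conflict.

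**A planned output gives a check.** The same table reports the responder comparison at Month 3, where fewer than 14 diary days means failure. This stands as a partial check. It is exploratory, does not gate, and misses those who stop late in Month 3 with 14 or more diary days.

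**No material effect is shown.** This also stands: every rate in the illustration is assumed.

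**Stronger readings to avoid.** A reader might infer that the rule favours rimegepant, or that the difference is biased whenever discontinuation or partial-data response differs between arms. The documents support neither, as no rates are given and the second row above is a counterexample. A reader might also infer that the primary is compromised. It is not: it is estimated from monthly values in the repeated-measures model, without this responder rule.

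**Conclusion.** The point holds as a contradiction between the declared estimand and its derivation, on an endpoint that gates others. Following SAP 6.3.2.1 as written judges an early stopper on pre-discontinuation days only, as few as 14, and can classify that subject as a responder for the full 12 weeks. That conclusion rests on the documents' rules alone. Its numerical effect is unknown in size and direction: each arm's rate rises by r×d, and the difference moves only if r×d differs between arms. It should be fixed, because the correction is cheap and the endpoint is confirmatory, but the documents do not show that the result would change.

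**What to change.** Before unblinding, reconcile SAP 3.2 and Table 2 with SAP 6.3.2.1 by one of two routes.

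1. **Keep the composite.** Add to the overall-DBT rule that a subject whose DB study drug last date (SAP 7.1) falls before the end of the 12-week phase is a failure. Define this from the drug date rather than from phase completion on the CRF, because SAP 6.2.3.3 counts a subject as a completer on a yes answer plus any non-missing last date. The sponsor should choose and justify in advance any tolerance for missed final tablets or missing end dates. The SAP supplies no ready-made one: the 11-week cut-off in SAP 6.2.6.1 is a rimegepant exposure category, not a completion rule. Apply the same condition to the exploratory overall-DBT responder endpoints, and keep the prorated version as a supplementary analysis.
2. **Keep the prorated rule.** Relabel the strategy as while-on-treatment in SAP 3.2 and Table 2, and add the composite version as a sensitivity analysis.

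Cost: SAP wording and one derivation from dates already collected, with no new data. Route 1 slightly lowers reported responder rates, by r×d in each arm. Route 2 leaves the main computed result unchanged but changes the stated estimand of a gated endpoint.
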